A Prospective Randomized Clinical Trial Comparing the Transversus
Abdominis Plane Block versus Epidural Anesthesia for Enhanced
Recovery Pathway Perioperative Management of Pain in Elective
Colorectal Surgery

NCT # 02591407

December 9, 2015

TABLE OF CONTENTS

1. BACKGROUND INFORMATION.....	5
2. STUDY OBJECTIVE.....	8
3. STUDY DESIGN.....	8
4. STUDY POPULATION	8
5. PATIENT RECRUITMENT & CONSENT.....	9
6. STUDY SCHEDULE	10
7. RANDOMIZATION.....	10
8. DATA COLLECTION AND MANAGEMENT	11
9. RISKS AND BENEFITS.....	11
10. SURGICAL PROCEDURE DESCRIPTIONS	14
11. STATISTICAL CONSIDERATIONS	18
12. QUALITY CONTROL AND QUALITY ASSURANCE	18
13. REGULATORY REQUIREMENTS.....	22
14 SCIENTIFIC REFERENCES.....	22
APPENDIX.....>	23

Protocol Summary	
Full Title	A Prospective Randomized Clinical Trial Comparing the Transversus Abdominis Plane Block versus Epidural Anesthesia For Enhanced Recovery Pathway Perioperative Management of Pain in Elective Colorectal Surgery
Short Title	TAP
IND Sponsor (if applicable)	St. Joseph Mercy Hospital Research Committee
Principal Investigator	[name]
Sample Size	176
Study Population	The study population will be composed of patient's \geq 18 years of age undergoing elective colon and rectal surgery for colorectal neoplasia, diverticulitis, and other diseases of the colon and rectum.
Accrual Period	Nov. 2015 – Feb. 2017
Study Design	Randomized trial comparing transversus abdominis plane block to epidural anesthesia for the management of perioperative pain in elective colorectal surgery
Study Duration	Nov. 2015 – Feb. 2018
Primary Objective	The primary outcome for this study is the Numeric Pain Score (NPS) for elective patients undergoing elective colorectal surgery in the Enhanced Recovery Pathway (ERP) program.
Risks/Benefits	The risks of this study are the same as those for patients receiving TAP blocks and epidural catheters outside of the study as well as the standard risks of colorectal surgery. TAP blocks and epidural analgesia are currently standard of care and widely employed at SJMH.

KEY ROLES

Institution: St Joseph Mercy Hospital
Address: [name]
[name]
Contact Person: [name] MD
[contact]
[contact]
E-mail: [contact]

Sponsor: SJMH Research Committee

Individuals: Principal Investigator:
[name] MD, Director Colon and Rectal Surgery ERI
Institution: St Joseph Mercy Hospital
Address: [name]
[name]
[contact]
[contact]
E-mail: [contact]

1. BACKGROUND INFORMATION

Adequate peri-operative analgesia is a vital component of post-operative management for patients undergoing colon and rectal surgery, affecting hospital length of stay, quality of life, and patient outcomes. There are many options for the peri-operative management of pain after elective colorectal surgery.¹ Randomized controlled trials have demonstrated improved perioperative pain management with epidural analgesia in postoperative colorectal patients when compared to intravenous and oral narcotic pain medications and are currently an integral component of Enhanced Recovery Pathway (ERP) programs. The benefit is believed to result from a decrease in the sympathetic overdrive that is associated with severe pain and surgical injury leading to decreased rates of ileus and fewer respiratory complications.² Epidural anesthesia is characterized by placing an epidural catheter into the epidural space at or below the level of the iliac crest (distal to the end of the spinal cord) prior to surgery. This catheter is secured to the patient's back and continuous analgesia (often bupivacaine) is administered from a pump. Risks of epidural analgesia are uncommon and include infection, bleeding, hypotension and bradycardia, urinary retention, and rarely temporary or permanent neurologic deficits.⁴

Other options for perioperative pain management include abdominal wall catheters placed either in the preperitoneal space at the time of surgery (OnQ®) or in the plane between the abdominal wall internal oblique and transversus abdominis muscles (TAP Block). A randomized controlled trial at this institution comparing epidural analgesia with the preperitoneal wound catheter pump (OnQ®) demonstrated that continuous epidural analgesia with bupivacaine provided better pain control on the day of surgery and on postoperative day one when compared to bupivacaine administered by the continuous preperitoneal pump.⁵

More recently, TAP Blocks that deliver bupivacaine in the plane between the internal oblique and transversus abdominis muscles have become popular in perioperative pain management for patients undergoing major abdominal open and minimally invasive surgery.⁶⁻⁷ The ease of insertion and advantage of a single injection without the need for an indwelling catheter make this option ideally suited for elective colorectal surgery patients. The disadvantage to this modality is the short duration of action. Peak levels for epidural and abdominal wall peripheral nerve block occur at 30-45 minutes with subsequent decrease to insignificant levels in 3 to 6 hours.

Bupivacaine is a local anesthetic drug belonging to the amino amide group. Bupivacaine is indicated for local anesthesia including infiltration, nerve block, epidural, and intrathecal anesthesia. Exparel® is a long acting bupivacaine local anesthetic FDA-approved for single dose infiltration for post-surgical analgesia. It is bupivacaine in a liposomal suspension that significantly increases the duration of action. The bupivacaine in this product is attached to a proven product delivery platform, DepoFoam®. A single intraoperative abdominal wall injection treats pain at the source with reduced opioid requirements for up to 72 hours, considerably longer than standard bupivacaine. When used as part of a multimodal treatment ERP regimen, Exparel® can provide non-opioid pain control that lasts as long as the most intense postsurgical pain, without the need for catheters, pumps, or other delivery devices.³ Exparel® has been shown to provide effective postsurgical analgesia when used in TAP Blocks.⁸

Because the duration of bupivacaine without liposomal suspension is short, there may be an advantage to using a long acting derivative such as Exparel® for TAP Blocks, especially with respect to decreasing narcotic pain medication needs after the first postoperative day.

This study compares two well-established treatment options within the context of a colon and rectal surgery ERP. Though both of these pain management options are utilized on a daily basis and considered standard of care in colorectal surgery, these two important pain treatment options have not yet been compared in a randomized controlled prospective trial. Epidural catheters are widely used for elective colon and rectal surgery and have the rare risk of central nervous system infections. If TAP Blocks are shown to be as effective as epidural analgesia in a randomized controlled study, this may result in a significant change in pain management for this patient population with the decreased associated risk. A significantly larger group of patients will likely receive Exparel® TAP Blocks rather than epidural catheters with the associated decrease in risk. Exparel® TAP Block would also be a reasonable option for those who are not candidates for epidural catheters (spinal stenosis, spinal fusion, patient refusal).

The outcome of this study will be considered meritorious scholarly activity and will be published in a peer-review journal. It will serve as a template for other surgical pain management programs at other institutions.

Pain Management in the field of colon and rectal surgery is rapidly changing and is undergoing constant re-evaluation. New information from this study will add considerably to the advancement of pain management programs in this field.

2. STUDY OBJECTIVE

The primary outcome is this study is the well-established Numeric Pain Score (NPS). A secondary outcome is the Overall Benefit of Analgesic Score (OBAS). This score was developed and validated by Lehman, et. al in 2010.⁹ OBAS is a comprehensive pain score that includes the variables of vomiting, dizziness, and sweating (Appendix 1).

Other secondary outcomes include perioperative narcotic requirements measured in morphine equivalents, hospital length of stay, time to first flatus, time to first bowel movement, and institutional costs of TAP and epidural interventions.

3. STUDY DESIGN

This is a physician-generated single-center randomized trial comparing TAP block to epidural analgesia for the perioperative management of pain in elective open and minimally invasive (laparoscopic and robotic) colorectal surgery.

4. STUDY POPULATION

Inclusion Criteria

- Patients undergoing elective open and minimally invasive (laparoscopic and robotic) colon and rectal surgery for colorectal neoplasia, diverticulitis, and other diseases of the colon and rectum;

- Surgical procedure either through standard open or minimal invasive approach (laparoscopic or robotic);
- Patients \geq 18 years of age;
- Able to provide informed written consent
- Patients capable of completing questionnaires at the time of consent

Exclusion Criteria

- Documented allergic reaction to morphine, hydromorphone, lidocaine, bupivacaine and/or fentanyl;
- Contra-indication to placement of epidural catheter (spinal stenosis, spinal fusion, elevated INR, anticoagulation, patient refusal, etc) or TAP block (patient refusal);
- Urgent or emergent surgery precluding epidural catheter placement or TAP block;
- Systemic Infection contraindicating epidural catheter placement or TAP block;
- Unwillingness to participate in follow up assessments;
- Prisoners
- Pregnant women

5. PATIENT RECRUITMENT & CONSENT

Due to the nature of this study; participants, nursing staff and the research team will not be blinded to randomization method. Standard analgesic options will be discussed with patients by the surgeons along with operative options, risks, and benefits, prior to scheduling operative intervention and per routine. The well-established Enhanced Recovery Pathway Program (ERP)

consists of patients with diseases of the colon and rectum seen in the surgeons clinic and inpatients on the Patient Care Unit. The ERP Nurse Navigator will review patient's records to determine which patients meet inclusion/exclusion criteria and are eligible to participate in the study. During the current pre-operative education classes, within ERAS, the Nurse Navigator will approach eligible patients and discuss the study. If the patient is interested, they will be given the opportunity to read the informed consent and ask questions regarding the study. Should they be willing to participate, the Nurse Navigator will obtain informed consent. Patients may also be consented in the surgeon's clinic by a research coordinator or investigator.

Informed consent and patient logs will be stored in the academic research department.

6. STUDY SCHEDULE

Patients will be asked their NPS and OBAS following consent during pre-operative education (baseline). NPS will then be obtained on operative day (0) and post-operative days 1, 2, and 3 from the electronic medical records that are documented by the patient care technicians every 8 hours. The OBAS will be collected by trained residents and nursing staff once a day on operative day (0) within 6 hours of recovery and between 0600 and 1200 on post-operative days 1, 2 and 3. If the patient is consented in the investigators office, pre-operative NPS and OBAS will occur there.

7. RANDOMIZATION

Two hundred patients will be randomized in blocks of ten with a 1:1 ratio. Standard open and minimally invasive (laparoscopic and robotic) approaches will have separate blocks. Patients

will be randomized using a web-based system called CREDIT. CREDIT maintains a patient log that includes randomization placement.

Randomization schedules were created using R (version 3.2.1), using 10 blocks were each selected has a 50% chance of being selected. The randomization process was conducted using box-muller to assign random numbers which was used to identify the selected treatment for each patient.

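### A fixed block size of ten in an open-label, single-centre trial could let a recruiter who tracks allocations know up to one in six in advance

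*Combined protocol and SAP*

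**What the plan says.** - **Block scheme (Section 7, Randomization).** "Two hundred patients will be randomized in blocks of ten with a 1:1 ratio". There are two strata: "Standard open and minimally invasive (laparoscopic and robotic) approaches will have separate blocks".
- **Assignment (Section 7).** Allocation is made through a web-based system, CREDIT, whose patient log records each assignment. Who may view the log is not stated. Nothing says that an assignment is released only once consent and stratum are on record.
- **A second description (Section 7, second paragraph).** This speaks of 10 blocks, a 50% chance of selection and Box-Muller random numbers. It does not clearly describe the same scheme as the first sentence.
- **Centre (Section 3, Study Design).** "This is a physician-generated single-center randomized trial".
- **Blinding (Section 5, Patient Recruitment & Consent).** "participants, nursing staff and the research team will not be blinded to randomization method".
- **Recruiters (Section 5).** The ERP Nurse Navigator screens records and approaches patients. "Should they be willing to participate, the Nurse Navigator will obtain informed consent". In addition, "Patients may also be consented in the surgeon's clinic by a research coordinator or investigator".
- **Outcome and sample size.** The primary outcome is the Numeric Pain Score, NPS (Section 2). Section 11 plans 176 patients, 53 laparoscopic and 123 open, and names a difference of 0.43 as the target. Section 7 gives 200 patients.

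**The concern.** In a 1:1 block of known size, once one arm has used its five places the rest of the block is determined. Web-based assignment hides the list, but it does not stop anyone deducing the next assignment from the block size and the allocations already made. Here the size is fixed and written in the protocol, there are only two sequences to follow, and a TAP block and an epidural catheter are readily told apart on the ward.

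The primary outcome is a patient-reported pain score in an open-label trial, so concealing the next allocation is one of the few protections against bias. If the next arm is known, expected pain or case complexity can influence who is approached and when. The target difference is small (0.43), so even modest steering could matter.

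**Working it through.** The plan gives no figure for predictability, so there is none to reproduce.

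**Inputs from the protocol.** Block size 10, 1:1, two strata, 200 patients (Section 7); 176 patients split 53/123 and target difference 0.43 (Section 11). Accrual from November 2015 to February 2017, 16 months (Protocol Summary).

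**Assumptions not in the protocol.** The recruiter knows the block size, or the set of sizes when they vary, and the full order of past allocations in the stratum. Steering changes the expected NPS of the enrolled patient by 0.5 points. Sizes 8, 10 and 12 are an illustrative alternative.

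**1. Allocations known for certain.** For a 1:1 block of 2m, the expected number of forced allocations is 2m/(m+1), a share of 1/(m+1).
- With m = 5: 10/6 = 1.667 per block, or 1/6 = 16.7%. Enumerating all C(10,5) = 252 blocks gives the same result.
- Every complete block ends with at least one certain allocation: exactly one in 55.6% of blocks, two in 27.8%, three or more in 16.7%.
- 200 patients: 200/10 = 20 blocks; 20 × 1.667 = about 33.
- 176 patients: 53 and 123 give 5 + 12 = 17 complete blocks; 17 × 1.667 = about 28, and 28.3/176 = 16.1%. The three patients left over in each stratum cannot be forced.

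**2. Other readings of Section 7.** Ten blocks of 20 give 1/(10+1) = 9.1%. Independent 50% draws give 0%.

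**3. Effect of hidden, varying sizes.** These come from simulation, updating the recruiter's probabilities after each allocation. The best-guess rate for fixed blocks is also exact: [5 + 2^9/252 − 0.5]/10 = 0.653.

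| Scheme | Certain | Guess held with over 80% confidence | Best guess correct |
|---|---|---|---|
| Fixed 10 | 16.7% | about 17% | 65.3% |
| Random 8/10/12 | about 1.3% | about 12% | about 65% |

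**4. What this could mean for the treatment comparison.** Let s be the shift, c the share certain and g the best-guess rate.
- *Steering only when certain, opposite directions by arm:* bias = 2 × c × s. Fixed: 2 × 0.167 × 0.5 = 0.17, which is 39% of 0.43. Varied: 2 × 0.013 × 0.5 = 0.01.
- *Steering only when certain, one direction:* bias = c × s. Fixed: 0.167 × 0.5 = 0.08 (19% of 0.43). Varied: 0.013 × 0.5 = under 0.01.
- *Steering on every best guess, opposite directions:* bias = 2 × s × (2g − 1). Fixed: 2 × 0.5 × (2 × 0.653 − 1) = 0.31. Varied, with g = 0.649: 2 × 0.5 × (2 × 0.649 − 1) = 0.30.

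All of these scale linearly with s. In the first case with fixed blocks, s = 0.25 gives 0.08 and s = 1.0 gives 0.33.

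**5. Feasibility of counting.** 176/16 = 11 patients a month overall, but blocks run by stratum: 123/16 = 7.7 a month for open and 53/16 = 3.3 for laparoscopic. A block of ten therefore lasts about 1.3 months in the first and about 3 months in the second.

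**The case against.** **The fix does little against ordinary guessing.** This stands. A recruiter who acts on every best guess causes nearly the same bias under either scheme (0.31 against 0.30). A reader might infer from the fall of 0.17 to 0.01 that varying the sizes removes the problem. That holds only if recruiters act solely on certain allocations, and the protocol says nothing about how recruiters would behave.

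**Recruiters may not see the allocation history.** This stands in part. A reader might infer that those who consent patients see every past allocation. Section 5 says they are unblinded, and Section 7 says a log exists, but neither says that the Nurse Navigator, coordinator and investigators each hold the full ordered history by stratum. With several recruiters, one person's next patient need not take the next place. The 16.7% is therefore a ceiling. It remains attainable at one site, with one main recruiter, treatments that are easily told apart and no stated limit on access.

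**The block size was not necessarily public.** Correct. The protocol states the size, and study staff can be presumed to have the protocol. The documents do not show that it was publicly available during accrual.

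**Ten is already a large block.** True: fixed blocks of 4 or 6 would give 33% or 25%. One in six is still avoidable.

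**The list may already be in use.** Section 7 describes the schedules as already made, and the document is dated December 2015, after the planned start of accrual in November. The change may therefore affect a live schedule and must be staged.

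**Conclusion.** The concern holds as an exposure. On the first sentence of Section 7, up to 16.7% of allocations (about 33 of 200, or 28 of 176) could be known in advance by a recruiter who knows the block size and tracks past allocations within a stratum. The figure would be 9.1% or 0% if the second paragraph describes the scheme actually used, so the two must be reconciled.

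A reader might go further and infer that selection bias occurred. The documents do not support that: they contain no evidence of steering and do not say who can view the log. The bias figures depend on an assumed 0.5-point shift and on how recruiters act, and they illustrate scale only. Varying the sizes nearly eliminates certain allocations and reduces high-confidence guesses, but leaves best-guess prediction almost unchanged. The change is worth making because it is cheap, and it should go together with limits on access to past allocations.

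**What to change.** In Section 7:

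1. Replace the fixed size with randomly varying block sizes (for example 8, 10 and 12) within each approach stratum. If enrolment has begun, apply this from the next block.
2. Keep the sizes in a restricted file, out of the protocol that recruiters use.
3. Restrict recruiters' access to the CREDIT allocation log.
4. State that CREDIT releases each assignment only after consent and stratum are recorded.
5. Rewrite the second paragraph so that it describes the same scheme as the first.

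**Cost.** The list must be regenerated in R and reloaded in CREDIT, with the changeover documented if the schedule is live. The largest possible imbalance from an incomplete final block rises from 5 to 6 per stratum.

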8. DATA COLLECTION AND MANAGEMENT

Demographic, health, and hospital stay data will be obtained from the Quality Institute. Data that is unavailable through electronic queries will be collected from the electronic medical record by a study team member. A pharmacist will collect PCA pain medication data that cannot be obtained from an electronic query of Pharmacy databases. All data will be entered into REDCap by a research study team member. Data will be stored in a locked office and password protected computer. Only members of the study team will have access to patient identifiers. Identifiers will be removed prior to analysis. All identifiers will be stored by the research coordinator in a secure location. Identifiers will be destroyed seven years following the conclusion of this study. (Data collection sheets, including adverse events Appendix 2).

9. RISKS AND BENEFITS

Patients will have no direct benefit from participating in this study. Both perioperative pain management treatment options are standard of care at SJHM. Exparel® is approved by the FDA for abdominal wall infiltration for perioperative pain management, but is not on pharmacy formulary at this institution because of cost. If this study demonstrates benefit to Exparel® utilization in TAP Blocks, it will very likely become formulary.

Listed below are the descriptions and risks of TAP block with Exparel® and epidural.

TAP Block

Exparel®: General

Bupivacaine is a local anesthetic commonly used and standard of care for pain management with epidural catheters and transversus abdominis plane regional blocks. Exparel® is a long acting form of bupivacaine. The Exparel® dose used is 266 mg. The adverse event profile is as follows: The most commonly encountered acute adverse experiences to bupivacaine and all amide-type local anesthetics that demand immediate counter-measures are related to the central nervous and cardiovascular systems. High plasma concentrations of bupivacaine can occur from overdosage, unintended intravascular injection, or accumulation of bupivacaine in plasma secondary to decreased hepatic metabolic degradation of the drug or diminished plasma protein binding capacity due to acidosis, pathologically lowered plasma protein production, or competition with other drugs for protein binding sites. Although rare, some individuals have a lower tolerance to and are supersensitive to bupivacaine and other amide-type local anesthetics and may rapidly develop signs of toxicity at low doses.

Please see attached Exparel® prescribing information/package insert.

Epidural

The progression of pain fibers blocked by local anesthetics in the epidural space proceeds in the following order from first to last; sympathetic tone, pain, temperature, proprioception, touch and finally motor. As a result there is a dose-dependent relationship between epidural-based local anesthetics and hemodynamic effects, as well as pain control. Sympatholytic dermatomal spread exceeds that of both pain control and that of motor blockade. Significant hemodynamic changes

can result, as venous capacitance increases in the dermatomes blocked. This may result in potential hypotension if intravascular volume is not increased to match this hemodynamic effect. When the dermatomal levels include the cardiac accelerator fibers above T6, bradycardia can also result.

In addition to hemodynamic changes, there are several other potential complications associated with epidural catheters. Inadvertent dural puncture occurs with an incidence ranging from 1-10%. The consequence is a positional headache, requiring the patient to lay supine until symptoms reside. Treatment is usually conservative, however epidural blood patch may be offered if symptoms are refractory to bed rest. Rare but more consequential complications include epidural hematoma and abscess. The American Society for Regional Anesthesia (ASRA) has published restrictions for epidural catheters based on INR, platelet count, and the presence of certain anticoagulants. Epidural abscess can result from epidural placement in a systemically infected patient. Lastly, neuropraxia may result from epidural catheters. However the incidence of this complication is both rare and self-limited (less than 30 days).

Opioids are also used with local anesthetic (LA) in the epidural space for analgesia. Opioids cross the dura rapidly and enter the spinal cord, where it binds with strong affinity to the opioid receptors in the substantia gelatinosa. The lipid solubility is a very important factor that effect the passage of opioids across the dura. Lipid-soluble drugs penetrate the spinal cord rapidly. Fentanyl is the commonly used opioid in epidurals due to it is a potent lipid soluble opioid with a strong affinity for the opioid receptor. Because of the reduced cephalic spread there are less opioid side effects with fentanyl. Pruritus is the most common side effect, while nausea and vomiting are less common. Respiratory depression is very rare and are usually associated with the use of other systemic opioids or its accumulation from an infusion.

